We expect challenges in following up with this cohort 2 years after the Year 0 clinic visit. We will employ several retention strategies between Years 0 and 2 that have been successful in prior trials, including mailing birthday cards to child participants, sending quarterly newsletters on family and children's health topics, inviting families to the annual Pennington Biomedical 5K, and telephoning the parent 2 months prior to the Year 2 clinic visit to schedule the visit and answer questions. The child will receive a stipend after each completed clinic visit and upon returning the accelerometer/GPS tracker, and the child will receive a certificate of completion upon finishing the study. Additionally, Pennington Biomedical has an excellent retention rate for clinical trials. The population of Baton Rouge is relatively stable, 82 and the majority of children will still be enrolled in K-12 school. Offering assessments during summer and school holidays will increase the likelihood of participation. We successfully followed up with children in prior prospective trials: 87% of children aged 10 to 14 years returned for a 2-year followup clinic visit in our Baton Rouge Children's Study (114 of the initial 131).77 Our retention for adult clinical trials is also excellent: we examined 14 trials conducted at Pennington Biomedical with a total of 1581 participants and observed a 70% retention rate over an average 4.8 year follow-up (range 1 year to 13 years). We expect an even higher retention rate due to the shorter follow-up time (2 years). Pennington Biomedical staff may contact participants every 3-6 months by phone or email to maintain contact between Year 0 and Year 2 clinic visits as well as schedule the Year 2 visit.

Anticipated Dropout

The 25% dropout rate is a combined estimate for both loss to follow-up and exclusions that occur during the clinic visit. Based on attrition at 2-year follow-up for Pennington Biomedical's Baton Rouge Children's Study,77 13% of the sample is expected to not report back for the 2-year follow up. An additional 12% is expected to be excluded due to exceeding weight limitations or the refusal of certain procedures (e.g. MRI, DXA) based on refusal rates in Pennington Biomedical's WAIST Study.20

Statistical Analysis

Objective 1:

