The hypotheses will be tested using a series of generalized linear models with severe obesity as the independent variable. First, linear mixed effect models will be used to test for effects between BMIz and each dependent continuous variable (change in: min/day sedentary behavior, min/day MVPA, and each cardiometabolic risk factor). Next, logistic regression models will be used to determine the association between BMIz with the likelihood of not meeting recommended behaviors (i.e. top quartile of min/day of sedentary behavior; MVPA < 60 min/day) or being at elevated cardiometabolic risk. Finally, the cohort will be stratified into two groups based on obesity at Year 0: severely obese (SO) and not severely obese (NSO). Logistic regression models will be used to determine associations between SO (vs. NSO) and each dependent variable (i.e. change in: minutes/day sedentary time, minutes/day MVPA, and each continuous cardiometabolic risk factor). Covariates will include age, sex, dietary intake, and race. School

term vs. school holiday will be considered as an additional covariate if time of year is significantly associated with the independent and dependent variables.

Secondary analysis will use MRI and DXA as covariates in the model (namely the visceral, trunk, and total body fat). These measurements, along with BMIz, may be highly correlated. Various variable select criteria (including LASSO and support vector machine) will be used to determine which combination of these variables best explains the variance in the data. The full model will enable the comparison of imaging-based body composition measures vs. BMIz alone and their associations with physical activity, sedentary behavior, and cardiometabolic risk factors in children.

As exploratory analyses, dietary intake will be tested as a potential mediator to explain significant associations between the predictor variable (BMIz) on outcomes (physical activity, sedentary behavior, and cardiometabolic risk factors). Series of sequential models will be used to test each pathway using a path analysis model based on the Baron and Kenny causal steps for mediation.73,74

Objective 2:

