The primary outcome for the first objective is change in minutes of sedentary behavior between Year 0 and Year 2 (i.e. Year 2 values minus Year 0 values). Baseline estimates for the two groups were calculated using the WAIST cohort data (from the 2010-11 assessment). Based on data from Berkey et al.,75 the SO group is assumed to increase their sedentary time by 30 minutes/day at year 2, while smaller increases in sedentary time is expected for the NSO group (**Table 5**). A minimum of 334 participants is needed to ensure a well-powered study with significance level of $\alpha = 0.05$, 80% power to detect a 24 minute difference change in sedentary behavior between the two groups, and allowing for a dropout rate of 25%. Therefore, our sample size of up to 345 participants will be sufficient.

Change in minutes/day of sedentary time for NSO group	Change in minutes/day of sedentary time for SO group	Difference in change between groups	Standard deviation of change between groups	Minimum sample size	Total sample size (allows for 25% dropout)
2.4	30.0	27.6	69.6	202	253
3.6	30.0	26.4	69.6	222	278
4.8	30.0	25.2	69.6	242	303
6.0	30.0	24.0	69.6	266	334

Table 5. Difference in changes in sedentary time based on severe obesity status. *Note.* NSO is the group classified as not severely obese; SO is the group classified as severely obese.

Note. NSO is the group classified as not severely obese; SO is the group classified as severely obese.

Secondary analyses will include change in daily MVPA minutes between years and change in days/week of physical activity (\geq 60 minutes MVPA/day) between years. Power analysis was conducted on these outcomes, using the WAIST cohort and data from Nigg et al.,76 and our sample size will have power of 93.8% and 90.4% to detect a significant difference in change in daily MVPA minutes and change in days/week of physical activity, respectively.

Contingencies

Based on national reference data, it is possible that very few or no severely obese children meet the healthy behavior or cardiometabolic health criteria (e.g. no severely obese child attains ≥ 60 minutes of MVPA/day; no severely obese child has a waist circumference < 90th percentile). If this is the case, the dichotomous dependent variable will be adjusted to be quartiles, so that the analyses is interpreted as the likelihood of a severely obese child being in the top (healthiest) quartile of the health behavior or cardiometabolic health criteria for the overall cohort.

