We will provide resources to participants to ensure that technical difficulties do not impede data collection (e.g. we will provide participants with a charger and regular reminders to charge the device to preserve power; we will provide a phone hotline and email address to provide technical assistance). It is possible that reactance may affect participants' responses, meaning that participants become more aware of behaviors, emotions, and cognitions as a result of being surveyed on a regular basis.108,109 Therefore, we will not assess behavior-specific cognitions, and we limit the number of survey questions and the frequency of the prompts.

Despite our numerous efforts to maximize participant compliance, we anticipate a small amount of missing data from the accelerometer, GPS, and EMA measurements due to participants not completely complying with the protocol by either not wearing the devices for a sufficient period of time or not responding to EMA survey prompts. Multiple imputation has been shown to work well with this type of data110 and will be used here. Sensitivity analysis will be conducted to determine if patterns exist in the missing data.

Data and Specimen Banking and Management

Blood samples will be banked for future research. These samples will be stored at Pennington Biomedical Research Center in a secure, locked storage freezer. Storage and disposal of biospecimens will be conducted in a manner conforming to the appropriate care and handling of biological specimens as outlined through the Institutional Biohazard Committee Guidelines. Only the investigators, study staff, and collaborators (including external to Pennington) explicitly given access to the samples by the principal investigator, will have access to these specimens.

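### Objective 1 fits a mixed model to one change score per child, so children who miss Year 2 contribute nothing and the severe-obesity contrast can be biased if dropout depends on Year 0 sedentary time

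*Combined protocol and SAP*

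**What the plan says.** The Objective 1 power analysis names the primary outcome as "change in minutes of sedentary behavior between Year 0 and Year 2 (i.e. Year 2 values minus Year 0 values". That is one number per child.

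Under Statistical Analysis, Objective 1, "linear mixed effect models will be used to test for effects between BMIz and each dependent continuous variable (change in: min/day sedentary behavior". No random effect, visit term or covariance structure is described. The adjustment set is given as "Covariates will include age, sex, dietary intake, and race", so Year 0 sedentary time is not in it. The SO versus NSO comparison is assigned to a different method: "Logistic regression models will be used to determine associations between SO (vs. NSO) and each dependent variable", where the dependent variables listed are continuous changes.

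On missing data, Anticipated Dropout says "13% of the sample is expected to not report back for the 2-year follow up". A further 12% covers weight limits and refused procedures, which makes up the 25% allowance. The Objective 3 contingencies say "we anticipate a small amount of missing data from the accelerometer, GPS, and EMA measurements due to participants not completely complying with the protocol", and plan multiple imputation for this plus a look for patterns in the missing data. Children with no Year 2 visit are not mentioned there. Withdrawal of Participants says that data already collected from withdrawn children will be used unless there is a request otherwise.

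**The concern.** A child-level random effect needs at least two records per child to be separated from residual error. With a single difference per child there is nothing for it to model, and the named mixed model becomes an ordinary regression. A child seen only at Year 0 has no outcome row, so that child's Year 0 record goes unused. This sits badly with the statement that withdrawn children's data will be used.

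At stake is the powered contrast. Change usually depends on the starting value: a child with a high Year 0 week tends to change less. If the children who leave differ in Year 0 sedentary time, and differ more in one group than in the other, the mean change among completers shifts unequally and the SO minus NSO difference moves with it. The background section reports more sitting among obese youth, so a baseline gap is plausible, but the documents give no figure for it and none for how dropout relates to it.

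**Working it through.** **Inputs from the documents.** Difference in change 24.0 min/day (30.0 SO, 6.0 NSO), SD of change 69.6, α 0.05, power 80% (Table 5 and the text above it); about half the sample SO; up to 345 enrolled; 13% not returning.

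**Assumed, not in the documents.** Year 0 to Year 2 correlation ρ of 0.3 to 0.7 (0.4 to 0.6 as the central range); SO baseline 0 to 60 min/day above NSO; dropout log-odds of 0.5 or 1 per SD of Year 0 sedentary time; a two-sided test.

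**Step 1: the plan's own figure.** Per group, n = 2 × (1.96 + 0.8416)² × 69.6² / 24² = 2 × 7.849 × 8.41 = 132.02, so 133 per group and 266 in total. This matches Table 5. The study is therefore sized as a comparison of one change score per child.

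**Step 2: standard error.** At 13% loss, 345 × 0.87 ≈ 300 children have a change score, and SE = 69.6 × √(4/300) = 8.0. At 266 children it is 69.6 × √(4/266) = 8.5.

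**Step 3: how the bias arises.** With equal variances at the two visits, expected change given the Year 0 value is δ − (1 − ρ)(Y0 − μ), where δ is the group's true mean change and μ its Year 0 mean. Let m be the completers' mean Y0 minus the group's mean Y0. The completers' contrast is then off by −(1 − ρ)(m for SO − m for NSO). It is zero when m is the same in both groups, however strongly dropout depends on Y0.

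**Step 4: size at 13% loss.** Bivariate-normal simulation with 400,000 children per group and true contrast 24. Simulation error is about 69.6 × √(2/348,000) ≈ 0.17. Entries are the change-score contrast among completers.

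| Dropout relation to Year 0 value | SO baseline gap | ρ = 0.3 | ρ = 0.5 | ρ = 0.7 |
|---|---|---|---|---|
| Same in both groups, log-odds 1 | 0 | 23.9 | 24.2 | 24.2 |
| Same in both groups, log-odds 0.5 | 30 | 24.4 | 24.5 | 24.3 |
| Same in both groups, log-odds 1 | 30 | 25.5 | 25.4 | 24.9 |
| Same in both groups, log-odds 1 | 60 | 27.2 | 26.3 | 25.8 |
| SO only, log-odds 0.5 | 0 | 26.6 | 26.4 | 25.6 |
| SO only, log-odds 1 | 0 | 29.6 | 28.8 | 27.4 |
| SO only, log-odds 1 | 60 | 30.5 | 29.2 | 27.9 |

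A joint model of both visits that keeps children seen only at Year 0 gives 23.8 to 24.4 in every 13% setting.

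In the central range of ρ (0.4 to 0.6), separate runs gave:
- SO-only dropout: 25.8 to 28.3, or up to 28.9 depending on how the 13% is split between the groups.
- A shared relation with a 30 to 60 min/day gap: 25.0 to 26.5, or as low as 24.3 when the relation is weak.

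If low-sedentary children are the ones who leave, the signs reverse.

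**Step 5: other dropout mechanisms, also at 13%.** If dropout follows a fixed latent level rather than the observed Year 0 week, the change score gives 23.9 to 24.3 and the joint model 21.0 to 22.5. If it follows the true Year 0 level, measured with an assumed reliability of 0.8, the change score gives 25.1 to 27.3 and the joint model 23.0 to 23.7.

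**Step 6: precision.** Where dropout is harmless, the joint model's SE is about 1 to 2% smaller at 13% loss.

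**The case against.** The strongest reply is that the plan does not say that incomplete children are dropped. A mixed model may be shorthand for a two-visit model, or for a family effect, since siblings can enrol and complete a sibling questionnaire. Multiple imputation is promised, and withdrawn children's data are to be used. All of this is possible, but none of it is written down. The random effect is not described, and the imputation is tied to incomplete wear and unanswered prompts. What stands is that the omission is one of specification and can be closed by wording.

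The second reply is that the change score has a virtue of its own. It cancels any stable child-level difference, so dropout that follows a child's usual level leaves it unbiased, while the joint model is pulled below 24. That stands in full. A reader might infer that the two-visit model rests on a weaker assumption and is always safer. Neither assumption contains the other, and Step 5 shows the ranking can flip.

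Third, the mixed-model sentence concerns BMIz, while SO versus NSO is given to logistic regression. That is correct. The loss of children without Year 2 applies to any model of the change score, but the contrast in the power statement, "80% power to detect a 24 minute difference change in sedentary behavior between the two groups", has no suitable linear model assigned to it. The fix has to supply one.

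**Conclusion.** The gap is real and modest. As written, the continuous Objective 1 analyses use only children with both visits, and the plan names no method for the 13% who do not return. The resulting bias in the SO versus NSO difference is conditional. It is about 1 to 4 min/day at 13% loss in the central settings, from 0.3 to 6.5 across the wider grid of differing groups, and zero when baseline level and dropout relation match. This compares with a target of 24 and a standard error of about 8. The correlation, baseline gap and dropout slopes behind these figures are assumptions.

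Two stronger readings are not supported. One is that dropout related to baseline biases the contrast in itself. It does not, because a relation shared by groups with the same baseline cancels. The other is that a quarter of the cohort lacks Year 2 data, which would put the change-score estimate at about 28 to 33 under SO-only dropout. Anticipated Dropout puts non-return at 13%. The other 12% concerns weight limits and refused procedures such as scans, and the Objective 2 contingencies say that over-limit children only have the scan removed. Nothing says they lose accelerometer data.

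**What to change.** For the continuous Objective 1 outcomes, state in the SAP:

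- Year 0 and Year 2 values enter as two records per child, with SO (or BMIz), time, their interaction, the listed covariates and a child random intercept, plus a family effect where siblings are enrolled. Covariates meant to adjust change, as they do in a change-score regression, also need a time interaction.
- Every child with at least one valid visit is included.
- SO by time is the estimate of the SO versus NSO difference in change, in place of the logistic regression now assigned to that continuous outcome.
- Multiple imputation of missed Year 2 values from Year 0 data is an acceptable equivalent. If it is chosen, the imputation paragraph should name children with no Year 2 visit.
- The completers' change score is kept as a sensitivity analysis.

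The cost is wording and some programming, with the same data and software. The downside is reliance on missing-at-random given Year 0, which is different from the change-score assumption and can itself give bias if dropout follows a stable latent level. That is the reason for keeping the sensitivity analysis.

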Precision medicine is an emerging medical model that customizes healthcare decisions based on an individual patient's characteristics, aimed at delivering the right treatment at the right time.² A population approach to precision medicine takes into account environmental exposures.³ As emphasized in the Scientific Report of the 2015 *Dietary Guidelines for Americans*,⁴ multiple determinants of health from an individual's physical and socio-emotional characteristics to the environment in which they live influence treatment adherence and efficacy. The "Exercise is Medicine" initiative calls for healthcare providers to prescribe physical activity for the prevention, treatment, and management of chronic diseases.⁵ An opportunity lies in leveraging precision medicine to create individualized physical activity plans for the prevention and treatment of obesity, a disease affecting 23% of Louisiana's children. To determine optimal, individually tailored exercise prescriptions, we must first identify the contexts within a child's day that facilitate physical activity and minimize time spent in sedentary pursuits, particularly among children with obesity. To achieve this aim, we will achieve the following objectives:

Objective 1: Determine the effect of severe obesity on physical activity, sedentary behavior, and cardiometabolic risk factors during childhood and adolescence and whether these associations are modified by race (NP 107, C4, PS 4A).

Hypothesis 1.A: Severe obesity will be associated with greater changes in physical activity, sedentary behavior, and cardiometabolic risk factors.

Hypothesis 1.B: Associations of severe obesity with physical activity, sedentary behavior, and cardiometabolic risk factors will be stronger among African American versus White youth.

Objective 2: Investigate the contribution of (total, regional, and depot-specific) fat accumulation on changes in physical activity, sedentary behavior, and cardiometabolic risk factors during childhood and adolescence (NP 107, C4, PS 4A).

Hypothesis 2: The accumulation of total, trunk, and visceral fat will be significantly associated with changes in physical activity, sedentary behavior, and cardiometabolic risk factors during childhood and adolescence.

Objective 3: Determine barriers and facilitators of physical activity that are related to obesity, including environmental and socio-emotional factors. (NP 107, C4, PS 4A).

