The Pennington Biomedical recruitment core will execute a plan to advertise through branches of the public library system, seek the support of community leaders, issue personal appeals through social organizations, place advertisements in places of congregation (i.e. libraries, churches), and conduct direct mailings, as well as advertisements via newspaper, radio, and television. Our recruitment plan is based on strategies that have resulted in investigators successfully reaching their recruitment goals: 1023 children and adolescents for cross-sectional obesity screening studies (Investigator [name])₁₆ and 1043 children and adolescents into physical activity and dietary interventions (Project Lead [name] and Investigator [name]).⁷⁸⁻⁸¹ Baton Rouge area has an estimated 2013 population of 445,277 and almost 46% of the population is African American.⁸² Even with anticipated loss to follow-up, we will have sufficient power in overall logistic regression analyses.

Recruitment will begin in the spring of 2016 and is expected to end in the spring of 2018.

Study Timeline

Participants will be enrolled on a continual basis over the course of 24 months. Participation in the study will last approximately 2 years. It is estimated that the investigators will complete primary analysis by December 2019. The study timeline is reported in **Table 1**.

		2016		2017				2018				2019		
	Q2	Q3	Q4	Q1	Q2	Q3	Q4	Q1	Q2	Q3	Q4	Q1	Q2	Q3
Personnel Training														
Participant Recruitment														
Baseline Testing, Y0														
Follow Up Testing, Y2														
Data Management														
Data Analysis Y0														
Paper Writing &														
Submission, Y0														
Data Analysis Y2														
Paper Writing &														
Submission, Y2														

Table 1. Study Timeline

Procedures Involved

Study Design

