Analyses to test Hypothesis 2 will be conducted using a series of linear regression models (i.e. linear mixed effects models). Based on difference score between Years 0 and 2 for total body fat, the group will be divided into two dichotomous groups using percentiles: high fat gainer (HFG) and low fat gainer (LFG). These variables will be used to predict changes in physical activity, sedentary behavior, and each cardiometabolic risk factor in linear mixed effect models. Covariates will include age, sex, dietary intake, and race. School term vs. school holiday will be considered as an additional covariate if time of year is significantly associated with the independent and dependent variables. Secondary analysis will use MRI and DXA as covariates in the model (namely the visceral, trunk, and total body fat). As previously reported, variable select criteria (including LASSO and support vector machine) will be used to determine which combination of these variables best explains the variance in the data. The full model will enable the comparison the accumulation of imaging-based body composition measures vs. BMIz alone and their associations with change in physical activity, sedentary behavior, and cardiometabolic risk factors in children. Finally, there are no standard accepted definitions of pediatric severe obesity to dichotomize participants based on MRI or DXA measures of body fat. Therefore, receiver operating characteristic curves will be created to estimate the value at which visceral, trunk, and body fat best correspond with the BMI definition of severe obesity (i.e. $BMI \ge 120\%$ of the 95th percentile1). Clinically relevant cut-points of severe obesity based on total, trunk, and visceral body fat will be established among this diverse cohort of adolescents.

Power analysis

Objective 1:

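### The severe-obesity contrast that sets the sample size is assigned a logistic model that cannot estimate it, and Hypothesis 1.B on race has no planned test

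*Combined protocol and SAP*

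**What the plan says.** Statistical Analysis, Objective 1, opens with "The hypotheses will be tested using a series of generalized linear models with severe obesity as the independent variable". It then names three sets of models:

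- linear mixed models for continuous changes, with BMIz as predictor;
- logistic models for binary outcomes (top-quartile sedentary time, MVPA below 60 min/day, elevated cardiometabolic risk), with BMIz as predictor;
- for SO against NSO: "Logistic regression models will be used to determine associations between SO (vs. NSO) and each dependent variable (i.e. change in: minutes/day sedentary time". The list goes on to change in MVPA and in each continuous risk factor.

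On adjustment it says "Covariates will include age, sex, dietary intake, and race".

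Power analysis, Objective 1, makes the primary outcome the Year 2 minus Year 0 change in sedentary minutes. It sizes the study for "80% power to detect a 24 minute difference change in sedentary behavior between the two groups, and allowing for a dropout rate of 25" percent. Recruitment Methods says that "we will have sufficient power in overall logistic regression analyses".

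For the parallel comparison of high and low fat gainers, Objective 2 says "These variables will be used to predict changes in physical activity, sedentary behavior, and each cardiometabolic risk factor in linear mixed effect models".

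Study Objectives asks, within Objective 1, "whether these associations are modified by race". Hypothesis 1.B reads "Associations of severe obesity with physical activity, sedentary behavior, and cardiometabolic risk factors will be stronger among African American versus White youth".

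**The concern.** There are two gaps between what Objective 1 asks and what its analysis section would deliver.

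**The primary contrast.** The only named model that uses the SO/NSO grouping is a logistic one, and its listed dependent variables are continuous. An analyst must either make SO the outcome, which reverses the declared independent variable, or split change at a cut-point the plan does not give. Neither returns the min/day difference behind the sample size. The choice could also be made after the data are seen.

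**Hypothesis 1.B.** An additive race term lets mean change differ by race but forces the SO effect to be the same in both groups. It cannot show whether the SO association is stronger in one. One of the two Objective 1 hypotheses therefore has no test. If an interaction is added later without warning of its width, a null result could be read as showing no difference by race.

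**Working it through.** **Inputs.** From Power analysis, Objective 1 and Table 5: difference 24 min/day (SO +30, NSO +6), SD of change 69.6, alpha 0.05, 80% power, 25% dropout, up to 345 enrolled. From Number of Participants: about 50% SO. Completers: 345 × 0.75 = 258.75, taken as 258 (129 per group).

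**1. Reproduce Table 5.** A two-sided two-sample t-test with SE = 69.6 × √(4/N) gives:

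| Difference (min/day) | Table 5 minimum N | Power at that N |
|---|---|---|
| 27.6 | 202 | 0.801 |
| 26.4 | 222 | 0.803 |
| 25.2 | 242 | 0.801 |
| 24.0 | 266 | 0.800 |

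All four rows reproduce, so the design assumes a comparison of two means. At 258 completers, power for 24 min/day is 78.8%.

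**2. Logistic, SO as outcome.** With normal changes and a common SD, the log odds ratio per minute is 24/69.6² = 0.00495, an odds ratio of about 1.005. Simulated power at 258 is 78.5%. The test is nearly as strong, but the estimate is not in min/day.

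**3. Logistic, change dichotomised** (cut-points assumed; two-proportion formula, 129 per group).

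| Assumed cut | SO vs NSO above cut | Odds ratio | Power | Completers for 80% |
|---|---|---|---|---|
| Median, 18 min | 56.8% vs 43.2% | 1.74 | 59.5% | about 418 |
| Top quartile, 65.6 min | 30.4% vs 19.6% | 1.80 | 52.1% | about 498 |

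Against 78.8%, the loss is 78.8 − 59.5 = 19.3 points or 78.8 − 52.1 = 26.7 points. Simulating the logistic model gave slightly lower power at both cuts (58–59% and 50.7%). Table 5 allows 266.

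**4. SO × race interaction.** SE = 69.6 × √(sum of 1/n over the four cells). At 258 completers (254 df), the detectable effect at 80% power is about 2.81 × SE and the 95% CI half-width is 1.97 × SE.

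| African American share of SO / NSO | SE | Detectable | Half-width | Power for 24 |
|---|---|---|---|---|
| 50% / 50% (equal cells of 64.5) | 17.3 | 48.7 | 34.1 | 28% |
| 63% / 37% | 18.0 | 50.5 | 35.4 | 26% |
| 72% / 28% | 19.3 | 54.2 | 38.0 | 24% |
| 75% / 25% (assumed) | 20.0 | 56.3 | 39.4 | 22% |

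The 63% and 72% rows use the 2 to 3 times higher prevalence in Description of Problem to be Solved and the 46% population share in Recruitment Methods: 0.46r/(0.46r + 0.54), with r = 2 or 3. This treats the other 54% as White (an assumption) and holds the whole sample at 50% African American. The documents give no expected interaction, so 24 min/day is illustrative. Detecting it with 80% power in equal cells would take 16 × (69.6 × 2.80/24)², about 1,056 completers.

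**5. Search for a test of 1.B.** From the Objective 1 analysis to the end of Objective 3, race appears only in the covariate lists for Objectives 1 and 2. The only baseline stratification is SO/NSO.

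**The case against.** The logistic sentence is probably a slip. The opening sentence names generalized linear models with SO as the independent variable, a class that includes the linear model wanted here. The power section fixes the outcome and contrast, and Objective 2 uses linear mixed models for its own two-group comparison. The Contingencies paragraph under Power analysis, Objective 1, describes SO models for binary health criteria, which suggests a misplaced variable list. The power loss arises only if change is dichotomised, which the text does not say. The recruitment sentence on logistic power may refer to the planned binary outcomes.

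Most of this is fair, but it explains the error without removing it. The generic opening also covers logistic regression, and the specific sentence then selects it. The contingency concerns meeting criteria and gives no cut-point for two-year change. No logistic power calculation is shown anywhere.

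The figure of 258 may also be low. Anticipated Dropout splits the 25% into 13% loss to follow-up and 12% for weight limits or refused procedures such as scans, which accelerometer data do not need. With 345 × 0.87 ≈ 300 completers, power for 24 min/day is 84.5%, dichotomised power about 66% and 58%, and the detectable interaction about 45 min/day. Device non-wear would pull 300 down, and the power section itself applies 25%.

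The imbalance rows are assumptions. Recruitment aims for a comparable race distribution, and the earlier cohort that supplies many recruits was balanced by race and obesity status, though not by severe obesity specifically. None of this supplies a test of Hypothesis 1.B.

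**Conclusion.** Both parts hold, and both should be corrected before analysis.

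The named SO/NSO model does not estimate the 24 min/day difference that justifies the sample size. The sample-size arithmetic for the minimum of 266 is sound as a comparison of means; the fault is in the model sentence. The main harm is a wrong or undefined estimand. A power loss of roughly 19 to 27 points follows only on the dichotomised reading with assumed cut-points.

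Hypothesis 1.B has no planned test. Adding one gives an estimate but not good power: about 49 min/day detectable at 258 completers in equal cells, about 45 at 300, and up to about 56 at 258 under the imbalance considered. All are well above the 24 min/day main effect.

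These figures assume SD 69.6 in every cell, equal SO and NSO groups and independent children. The Sibling Relationship Questionnaire section shows that siblings may be enrolled, and the documents give no number. A short part of the document outside the statistical sections was unavailable; the analysis and power sections were complete.

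**What to change.** 1. Replace the SO/NSO logistic sentence with a linear model of change in sedentary min/day, and of each other continuous change, on SO plus the listed covariates. Alternatively, use a linear mixed model of the two visits with SO × visit and covariate-by-visit terms. Name the adjusted SO–NSO difference in min/day, with its 95% CI, as the primary Objective 1 result.
2. Keep logistic regression for the binary outcomes: top-quartile sedentary time, MVPA below 60 min/day and elevated cardiometabolic risk. Align the power sentence in Recruitment Methods with the power section, or support it with a calculation.
3. Add SO × race (SO × race × visit in the mixed model) as the test of Hypothesis 1.B, reported with its 95% CI. State in advance that it is imprecise: about 49 min/day detectable with 80% power at 258 completers with equal cells and SD 69.6, about 45 if 300 complete, and more if race is unbalanced across SO and NSO. State that a non-significant interaction will not be read as no difference by race.

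The cost is a few sentences and one model term, with no new data. The drawback is an openly wide interval for 1.B: half-width about 34 min/day with equal cells, and about 39 at 75%/25%, both at 258 completers.
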